#### 7.4.1.1 Primary Efficacy Analysis

The primary analysis will use a pMMRM approach (G. Wang et al., 2022). The details of the pMMRM are presented below. Conceptually, the pMMRM is similar to the Cox proportional hazards model, as it models the treatment effect as a single proportional difference at each post-baseline visit. It uses time as a categorical variable like an MMRM and thus avoids the linearity assumption. On the other hand, pMMRM takes on the assumption of a proportional treatment effect of a linear mixed-effect (LME) model and thus uses assessments more efficiently than an MMRM model (Table 7-20).

Protocol No. AL002-2 Last Revision Date: 12 Aug 2025

Let  $y_{ijk}$  denote the longitudinal assessments for participant i at time j for treatment group k,  $i = 1, 2, ..., n_k$ ,  $j = 0, 1, ..., m_i$ , and k = 1, 2, 3, 4 represents the placebo group and one of the treatment groups. Specifically, let k = 2 denote the treatment group of AL002 15 mg/kg; k = 3 denote the treatment group of AL002 40 mg/kg; k = 4 denote the treatment group of AL002 60 mg/kg.

The marginal pMMRM which evaluates the treatment effect of the 3 treatment groups simultaneously can be written as:

$$\Delta y_{ijk} = \beta_0 (y_{i0k} - \bar{y}_0) + \Delta_{j1} (1 - \theta_k) + \varepsilon_{ijk}$$

where  $\Delta y_{ijk}$  is the individual change from the baseline  $y_{i0k}$  and is calculated as  $y_{ijk} - y_{i0k}$  for  $j = 1, ..., m_i$ .  $\beta_0$  is an unknown parameter which represents the association between  $y_{i0k}$  and  $\Delta y_{ijk}$ .  $\bar{y}_0$  is the marginal mean of the baseline values of both the treatment groups and the placebo group, and the inclusion of  $\bar{y}_0$  enables the model to provide a treatment effect adjusted for the baseline value.  $\bar{y}_0$  is the arithmetic mean of the baseline values of the treatment groups and the placebo group when the design is balanced (e.g., equal sample size for both groups); and is the marginal mean when the design is unbalance (e.g., missing data lead to different sample size in the two groups). For unbalanced design,  $\bar{y}_0$  is the same as the one used in the MMRM least square mean estimation and can be obtained through the MMRM model. Parameters (to be estimated) include  $\Delta_{j1}$ , the mean CFB for the placebo group at time j for  $j \ge 1$ ,  $\theta_k$ , the proportional treatment effect for group k with  $\theta_k = 0$  for the placebo group, and  $\varepsilon_{ijk}$ , the within-participant error, which is assumed to follow a multivariate normal distribution:

$$N\begin{pmatrix} 0 \\ 0 \\ \vdots \end{pmatrix}, \Sigma_{m_i \times m_i}$$
, where  $\Sigma$  is an unstructured variance-covariance matrix and  $m_i$  is the number of repeated post-baseline measures for participant  $i$ .

If the treatment has no effect at all, then the primary endpoint  $y_{ijk}$  will progress at the same rates after baseline for the treatment group and the placebo group, leading to  $\theta_k = 0$ ; if the treatment completely stops the disease progression, then  $y_{ijk}$  will not progress after the baseline in the treatment group, leading to  $\theta_k = 1$ ; if the treatment worsens the disease progression, then  $y_{ijk}$  will progress faster after the baseline in the treatment group than that in the placebo group, leading to  $\theta_k < 0$ ; and if the treatment slows the disease progression, then  $y_{ijk}$  will progress slower after the baseline in the treatment group than that in the placebo group, leading to  $\theta_k > 0$ .

Table 7-20. Comparisons of Statistical Models

Models	Linearitya	Time Variable	Treatment Effect	Extended Follow-up
MMRM	No	Categorical	Non-proportional	Yes b
pMMRM	No	Continuous/Categorical	Proportional	Yes

<sup>a refer to the assumption between time as a continuous variable and outcome variable.

Like MMRM, the parameters in the marginal pMMRM model can be estimated using the (restricted) maximum likelihood method.

<sup>b when using an MMRM model to obtain estimates at a specific key timepoint, data beyond the key timepoint of interest don't directly contribute to the statistical inference at the key timepoint.

Protocol No. AL002-2 Last Revision Date: 12 Aug 2025

The unstructured covariance matrix will be used to model within-participant variance and covariance. The estimates of  $\Delta_{j1}$ ,  $\beta_0$  and  $\Sigma$  from MMRM will be used as the initial values of pMMRM to facilitate model convergence. If the unstructured covariance matrix results in a lack of convergence, the following structures will be used in sequence:

- Heterogeneous Toeplitz (TOEPH) covariance structure,
- Heterogeneous first-order autoregressive (ARH(1)) covariance structure,
- Heterogeneous compound symmetry (CSH) covariance structure,
- Toeplitz (TOEP) covariance structure,
- First-order autoregressive (AR(1)) covariance structure,
- Compound symmetry (CS) covariance structure.

In the case that a structured variance-covariance matrix is used to enable the model to converge, the "sandwich" estimator of the variance-covariance matrix will be employed by using the "empirical" option in the SAS PROC MIXED procedure.

The Kenward-Roger method will be used to calculate the denominator degrees of freedom for the test of fixed effects and adjusted standard errors. If the pMMRM that models all three treatment groups simultaneously fails to converge after exploring all the above options, pMMRM will be applied to each treatment group to estimate the treatment effect for each dose separately.

The estimated proportional treatment effect and its 90% and 95% CIs will be reported from the final fitted model.

Additionally, the same analysis described above will be repeated with the following groups in the model: AL002 15 mg/kg group, AL002 40 and 60 mg/kg combined group, and placebo group. All statistics described above from fitting the model will be reported only for the AL002 40 and 60 mg/kg combined group (or its comparison to placebo).

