#### 3.2 Randomization

Participants in Part 1 (approximately 40 participants total) will be randomly assigned on or prior to the Predose Baseline visit (if applicable), or on or prior to the Day 1 visit (if there is no Predose Baseline visit), by stratification on APOE e4 status (e4 carrier vs non-e4 carrier) to receive 15 mg/kg AL002, 40 mg/kg AL002, 60 mg/kg AL002, or placebo in an overall 1:1:1:1 allocation ratio. Participants in Part 2 (approximately 288 participants total) will also be randomly assigned on or prior to the Predose Baseline visit (if applicable) or on or prior to the Day 1 (if there is no Predose Baseline visit) by stratification on APOE e4 status (e4 carrier vs non-e4 carrier) to receive 15 mg/kg AL002, 40 mg/kg AL002, 60 mg/kg AL002, or placebo, using a 1:1:1:1 allocation ratio. An interactive web response system will be used to administer the randomization schedule. Further specific details will be described in the randomization specifications.

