## 7.4.1.2 Supportive Analysis using Mixed-Effects Model for Repeated Measures (MMRM)

A restricted maximum likelihood based MMRM will be used as a supportive analysis to assess the primary endpoint.

The SAS® MIXED procedure will be used to fit an MMRM with CFB in CDR-SB at each scheduled post-baseline visit (Week 24, 48, 72, and 96) as the dependent variables and the fixed effects will include following items:

- Treatment group,
- Visit (categorical, as week),
- Visit-by-treatment interaction,
- Baseline CDR-SB score (covariate),
- APOE e4 status (covariate, e4 carrier vs non-e4 carrier).

An unstructured covariance matrix will be used to model within participant variance-covariance errors. If the unstructured covariance structure matrix results in a lack of convergence, the following tests will be used in sequence:

- Heterogeneous Toeplitz (TOEPH) covariance structure,
- Heterogeneous first-order autoregressive (ARH(1)) covariance structure,
- Heterogeneous compound symmetry (CSH) covariance structure,
- Toeplitz (TOEP) covariance structure,
- First-order autoregressive (AR(1)) covariance structure,
- Compound symmetry (CS) covariance structure.

In the case that a structured variance-covariance matrix is used to enable the model to converge, the "sandwich" estimator of the variance-covariance matrix will be employed by using the "empirical" option in the SAS PROC MIXED procedure.

The Kenward-Rogers approximation will be used to estimate the denominator degrees of freedom when the covariance is unstructured.

Least squares means (LSMs) and their difference between each treatment group and the placebo will be estimated for Week 24, 48, 72, 96 and "overall" (the average of Week 24, 48, 72, and 96) for each of CDR-SB. The LSMs are interpreted as the expected CFB in the primary efficacy outcome. LSMs and standard errors (SEs) will be shown for each active treatment group and placebo. In addition, the percent slowing of decline expressed as the ratio of negative difference in LSMs over the LSM of placebo (i.e., [(–difference in LSM) / (LSM of placebo)] × 100%) will be displayed for each active treatment group. And its CI will be derived using the Delta method (refer to APPENDIX for more details on the derivation).

LSMs line plots over time will be displayed for the primary endpoint with separate lines for each treatment group.

Protocol No. AL002-2 Last Revision Date: 12 Aug 2025

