#### 7.7.1 PD Assessment Objective

#### 7.7.1.1 FAS

For exploratory PD biomarkers (CSF, plasma, amyloid PET, Tau PET and volumetric MRI) listed in Table 7-25 [subsets 1 and 2] in the FAS, their visit values, change from baseline (CFB) and percent change from baseline (PCFB) for the main estimand will be summarized by treatment group over time (all visits) using descriptive statistics (Table 7-26).

Comparisons of CFB between AL002 dose groups vs. placebo will be explored for the main estimand using MMRM models (see Section 7.4.1.2) with treatment group, categorical visit, visit-by-treatment interaction, baseline biomarker, and APOE e4 status of e4 carrier vs. non-e4 carrier as fixed effects (Table 7-26). Treatment comparisons will be reported for specified visits as indicated below:

- Plasma biomarkers:
  - O AD-pathology (Aβ42/40, pTau217, MTBR-Tau243): week 12, 24, 48, 72 and 96
  - o AD-pathology (pTau181): week 16, 36, 60 and 84
  - o Target engagement (IL1RA): week 1, 2, 4, 6, 8, 12, 24, 36, 48, 72 and 96
  - o Neurodegeneration (NfL, GfAP): week 12, 24, 48, 72 and 96
- CSF biomarkers: week 6, 48 and 72
- Amyloid PET parameters: week 48
- Tau PET parameters: week 48 and 72
- Volumetric MRI parameters: week 48, 72 and 96

Additionally, the same analysis for the main estimand described above will be repeated with the following groups in the model: AL002 15 mg/kg group, AL002 40 and 60 mg/kg combined group, and placebo group. All statistics described above from fitting the MMRM model will be reported only for the AL002 40 and 60 mg/kg combined group (or its comparison to placebo).

For Tau PET parameters [subset 1] in Table 7-25, a sensitivity analysis (main estimand) will be conducted with similar descriptive summaries and MMRM models for the subset with redefined baseline (either pre-dose Tau PET if evaluable or the first post-dose evaluable Tau PET scan if pre-dose PET scan

Protocol No. AL002-2 Last Revision Date: 12 Aug 2025

is missing) (Table 7-26). A pMMRM model (main estimand) will be additionally conducted for both subsets of true baseline and redefined baseline (Table 7-26).

Given the limited sample size mapped to the Week 96 analysis visit for CSF, Amyloid PET and Tau PET, this visit will only be summarized descriptively and excluded from modelling (i.e., pMMRM and MMRM).

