#### 7.7.2 Correlation with CDR-SB Objective

Treatment-related association between CFB in biomarker levels (CSF, plasma, amyloid PET and Tau PET) [subset 1] in Table 7-25 and CFB in CDR-SB will be assessed. Specifically, the following analyses will be conducted for the main estimand [Table 7-27].

- Adjusted correlative analyses of CFB in CDR-SB and CFB in specified subset 1 biomarkers. Three MMRM models will be assessed.
  - o Model 1 of CFB in biomarker with treatment group, categorical visit, visit-by-treatment interaction, baseline biomarker, and APOE e4 status as fixed effects.
  - o Model 2 of CFB in CDR-SB with the same fixed effects terms as in model 1, and baseline CDR-SB as additional fixed effects term.
  - o Model 3 of CFB in CDR-SB with the same fixed effects terms as in model 1, and baseline CDR-SB and CFB in biomarker as additional fixed effects terms.
  - o The three models include only participants with both CFB in CDR-SB and CFB in biomarker at matching timepoints.
  - Similar analyses will be repeated with the following treatment groups in the model: AL002 15 mg/kg group, AL002 40 and 60 mg/kg combined group, and placebo group. Statistics from fitting the MMRM model will be reported only for the AL002 40 and 60 mg/kg combined group (or its comparison to placebo).
- Group-level scatterplots of adjusted mean difference from placebo in CDR-SB and adjusted mean difference from placebo in specified subset 1 biomarkers at matching timepoints.
  - The adjusted mean difference from placebo is the least squares mean difference (vs. placebo) in the corresponding MMRM analyses.

Protocol No. AL002-2 Last Revision Date: 12 Aug 2025

- o Add the error bars (±SE) for adjusted mean difference from placebo in CDR-SB.
- o Include AL002 40 and 60 mg/kg combined group in the scatterplot.
- o Add Pearson and Spearman correlation coefficients, and linear regression line (exclude the combined group AL002 40 and 60 mg/kg).

For subset 1 Tau PET parameters in Table 7-25, a sensitivity analysis will be additionally conducted with similar analyses for the subset with redefined baseline.

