#### 9. CHANGES FROM METHODS PLANNED IN THE PROTOCOL

The statement of the primary estimand given in Section 6.2.1.2 clarified that the target population excludes e4/e4 participants, that the primary estimand specified in the latest version of the protocol did not specify this exclusion. This clarification does not result in any differences for summaries or analyses.

The criteria for PPS in Section 5.3.2 are updated as the one specified in the protocol was too general and did not meet the needs of PPS.

The summary of physical examinations will not be performed, since clinically significant physical examination changes will be captured in the AE summaries.

The supportive analysis using LME model is removed from this SAP. The primary analysis using the pMMRM model is based on the assumption of proportionality, which is an inherit assumption of the LME model. If the assumption of proportionality is not met under the pMMRM model, the results of analysis using the MMRM model will be used to interpret the study. For this reason, the supportive analysis using LME model has been removed from SAP.

Safety analyses will primarily be performed for the Non-e4/e4 Set, instead of the Safety Set as specified in the protocol, because of the removal of the e4/e4 participants from the participant population being studied. The AL002-2 study originally included enrollment of participants who were APOE e4 homozygotes (e4/e4). However, further enrollment of participants with this APOE genotype was permanently stopped after the evaluation of safety among the early enrolled participants with e4/e4. Therefore, the primary objective of the study changed to the assessment of AL002 in the participants without e4/e4.

The exploratory analyses of WLSA data (optional study) and genetics will be excluded from the SAP.

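### The primary pMMRM leaves out APOE e4 status, the only stated stratification factor, although the SAP's MMRM-type models of CDR-SB change include it

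*SAP*

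**What the plan says.** SAP 3.2 assigns participants in both parts "by stratification on APOE e4 status (e4 carrier vs non-e4 carrier"), 1:1:1:1, and names no other factor. Protocol 5.1 says the same.

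SAP 7.4.1.1 introduces the primary model with "The marginal pMMRM which evaluates the treatment effect of the 3 treatment groups simultaneously can be written as" and then gives it in full. Change from baseline equals β₀ times centred baseline CDR-SB, plus the placebo mean change at that visit times (1 − θ for the dose), plus error. The only covariate is baseline, centred because this "enables the model to provide a treatment effect adjusted for the baseline value". There is no e4 term.

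Other models of the same outcome do adjust:

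- The supportive MMRM in SAP 7.4.1.2 lists "APOE e4 status (covariate, e4 carrier vs non-e4 carrier") among its fixed effects.
- In SAP 7.7.2, Model 1 has "baseline biomarker, and APOE e4 status as fixed effects". The text then defines "Model 2 of CFB in CDR-SB with the same fixed effects terms as in model 1", and Model 3 inherits them too, so both models of CDR-SB change contain e4 status.
- The imputation regressions for CDR-SB in SAP 7.4.1.4 use e4 status, but the completed data then go into the pMMRM without it.

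The biomarker MMRMs in SAP 7.7.1.1 likewise have "baseline biomarker, and APOE e4 status of e4 carrier vs. non-e4 carrier as fixed effects".

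Protocol 8.3.2.1 names no covariates for the pMMRM and gives the MMRM baseline CDR-SB as its only covariate. The SAP therefore added e4 status to the MMRM and not to the primary model. Neither SAP 7.4.1.1, SAP Section 9 nor the version history gives a reason.

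**The concern.** A factor used to balance the randomisation would normally be in the primary model, or its absence explained. When arms are balanced within strata, the true sampling variance of the treatment contrast no longer contains the between-stratum component, but a model without the factor still counts it as noise. If e4 status is prognostic, the reported standard error is then too large, the test is somewhat conservative and some power is lost.

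The omission carries into every fit that reuses the model: combined-dose, supportive-estimand, post-imputation, per-protocol, secondary and subgroup.

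It also leaves the primary model and its fallback adjusted differently. SAP Section 9 says that if proportionality is not met, "the results of analysis using the MMRM model will be used to interpret the study". A difference between the two fits would then mix the proportionality restriction with a covariate difference.

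In addition, the Full Analysis Set removes e4/e4 participants after randomisation, and all of them come from the carrier stratum. Carrier balance in the analysed set is therefore not strictly guaranteed.

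**Working it through.** **The plan's own figures (SAP 3.5).** Sample size: 4 × 70 + 15 + 6 + 27 = 328, or 82 per group, as stated. The 83% power cannot be derived from first principles because the means and covariance are not given, but the table can be checked for consistency. The 60-per-group, 40% cell (78%) implies a noncentrality of 1.645 + 0.772 = 2.417. Scaling by √(70/60) gives 2.611, and Φ(2.611 − 1.645) = 83.3% against the stated 83%. The same scaling gives 62.3% (stated 64%) and 56.7% (stated 59%) for a 30% reduction at 70 and 60 per group.

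**Inputs for the comparison.** One-sided 5% test, z = 1.645 (SAP 7.4). Noncentrality at 83% power: 0.954 + 1.645 = 2.599. R², the share of residual variance explained by e4 status, is an assumption (1%, 3%, 5%).

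**Formulas, strata balanced across arms.**
- SE overstatement: 1/√(1 − R²) − 1
- Actual size without the term: 1 − Φ(1.645/√(1 − R²))
- Power without: Φ(0.954/√(1 − R²))
- Power with: Φ(2.599/√(1 − R²) − 1.645)

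| Assumed R² | SE overstated | Size without | Power without | Power with | Gain (points) |
|---|---|---|---|---|---|
| 1% | 0.5% | 4.9% | 83.1% | 83.3% | 0.2 |
| 3% | 1.5% | 4.7% | 83.4% | 84.0% | 0.6 |
| 5% | 2.6% | 4.6% | 83.6% | 84.7% | 1.0 |

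For scale, the Monte Carlo standard error of the plan's 83% is √(0.83 × 0.17/5000) = 0.53 points.

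**Simulation.** Four arms fitted jointly as in SAP 7.4.1.1; 70 per arm; missingness 22/27/44/58% (SAP 3.5); unstructured covariance by maximum likelihood; Wald test of one dose against placebo; 4,000 runs per scenario. Assumed, not from the documents: 55% carriers, balanced by arm; placebo means 0.6/1.3/2.1/3.0; SDs scaled to about 84% power at a 40% reduction.

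| Result | R² 1% | R² 3% | R² 5% |
|---|---|---|---|
| Power without / with the term | 84.1 / 84.2% | 84.2 / 84.8% | 84.4 / 85.3% |
| Ratio of mean SE, without to with | 1.005 | 1.016 | 1.028 |
| Correlation of the two θ estimates | 0.999 | 0.995 | 0.990 |
| SD of their difference | 0.008 | 0.014 | 0.020 |
| Trials in which the decision changes | 1.1% | 2.0% | 2.8% |
| Null rejection without / with | 8.65 / 8.72% | 8.43 / 8.62% | 8.05 / 8.62% |

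The mean θ estimate is 0.390 without the term and 0.390 to 0.391 with it; the estimate's SD is about 0.14 either way. When the e4 effect grows by visit but a constant coefficient is fitted (3,000 runs), power is 84.6% against 84.7% at R² of 1% and 85.0% against 85.8% at 5%.

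A second simulation with other assumed means (0.55/1.15/1.85/2.6; 1,500 runs) gave 84.7% against 84.9% when carriers and non-carriers differ by 25% of the placebo decline, and 83.3% against 83.9% at 50%. With no e4 effect it gave 85.2% against 85.3%, so the extra parameter costs nothing visible.

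**Coding matters.** θ multiplies the placebo mean. With a 0/1 indicator that is not centred, that mean becomes the decline of one stratum, and the mean θ estimate moves from 0.390 to 0.411 (R² 1%), or from 0.393 to 0.419 (R² 5%, growing effect).

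**The case against.** The strongest case against is that this is a modelling preference with almost no consequence. No document commits to adjusting the primary model for e4 status, and since the protocol names no pMMRM covariates, the primary model is not a departure from it. The undocumented change is the e4 term added to the MMRM, which one line in Section 9 would cover. The pMMRM fits are consistent among themselves; the split is between pMMRM and MMRM-type models. e4 status is already used in randomisation, in the MMRM, in the imputation regressions and as a subgroup. The magnitude rests on assumed R², means and carrier share, and nothing in the documents shows that e4 status is prognostic once e4/e4 participants are excluded. The SAP was last revised on 12 August 2025, and SAP 7.7.1.1 already refers to limited Week 96 numbers for CSF and PET, which is late to respecify a primary model.

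Much of this stands, and it is why the point is minor. The gain is small, conditional on R², and nil if R² is near zero. The simulated null rejection exceeds 5% with and without the term. That reflects an ML Wald test without Kenward-Roger under assumed inputs: it is not the size of the planned test, and the term does not cure it.

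What does not follow is that nothing should be done. That the protocol is silent does not explain why the SAP adjusts the fallback model and leaves the primary one unadjusted. The re-fits inherit the primary model's omission and do not count as independent evidence for it.

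**Conclusion.** The point holds and is minor. The only stated stratification factor is absent from the primary model, present in the MMRM and correlation models of the same outcome, and the difference is unexplained. Under balanced stratification θ is not biased, and the error is in the conservative direction. For an assumed R² of 1% to 5%, the loss is 0.2 to 1.0 points of power by formula and 0.1 to 0.9 in the main simulation, so the stated 83% is not undermined. Estimates with and without the term nearly coincide, so the mismatch with the MMRM does not materially obstruct a judgement on proportionality. Confidence in the size is medium because the documents supply neither R² nor the CDR-SB means and covariance.

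**What to change.** Before database lock, write the model in SAP 7.4.1.1 as

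Δy_ijk = β₀(y_i0k − ȳ₀) + β₁(a_i − ā) + Δ_j1(1 − θ_k) + ε_ijk,

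with a_i = 1 for e4 carriers, 0 otherwise, and ā the mean of a_i. Centring is required so that Δ_j1 remains the placebo mean and θ keeps its meaning.

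Use the same form for the combined-dose, supportive-estimand, post-imputation, per-protocol, secondary and non-APOE subgroup fits, including the pTau217 terciles. Drop the term within the APOE e4 subgroups, where it is constant. The covariates then match those of the MMRM. The two models may still differ in covariance structure, estimation method (7.4.1.1 permits full or restricted likelihood; 7.4.1.2 fixes restricted) and reported summary. Re-check type I error by simulation with the final model.

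If the sponsor prefers to leave the term out, one sentence in 7.4.1.1 should say why. The documents do not say whether lock has occurred; if it has, report the adjusted fit as a labelled sensitivity analysis.

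The cost is one model term for a covariate already collected, SAP wording and a re-run of the operating-characteristics simulation. Data collection and sample size do not change.
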